Average concentrations of antroquinonol in plasma with 200 mg TID antroquinonol treatment were uniformly higher on Day 28 than on Day 1. The mean C_{max} was 276.87 and 393.55 ng/mL for Days 1 and 28, respectively, and the mean area under the plasma concentration versus time curve (AUC) within a dosing interval (AUC_{tau}) was 790.9 and 1224.3 h*ng/mL. The average oral clearance for antroquinonol was higher on Day 1 (254.31 L/h) than on Day 28 (197.82 L/h). The mean values of $T_{1/2}$ on Day 1 and $T_{1/2,eff}$ on Day 28 were 1.617 and 7.643 h, respectively. The mean antroquinonol trough plasma concentration (C_{trough}) were 44.99 and 74.71 ng/mL on Days 1 and 28, respectively. Accumulation of antroquinonol following 28 days of 200 mg TID dosing was estimated to be 1.892-fold.

Phase 2 study (GHLIP-2-001) Hyperlipidemia

A total of 180 subjects were screened and 120 of them were eligible. Of the 120 enrolled subjects, 30 each were randomly assigned to the placebo, antroquinonol 50 mg, antroquinonol 100 mg, and antroquinonol 150 mg groups. One hundred subjects completed the 12-week study treatment period. The main reason of discontinuation was the occurrence of adverse events (AEs) (15 out of 20, 75.0%).

Antroquinonol was generally well tolerated when administered at 50 mg, 100 mg, and 150 mg once daily for 12 weeks. During the study, 55.6% in the antroquinonol group and 46.7% in the placebo group reported at least 1 AE. All AEs, except one, were mild or moderate in severity. The most common AE occurring in the antroquinonol group and placebo group by system organ class (SOC) were gastrointestinal disorders, in which, diarrhoea was the most frequent AE reported in both antroquinonol and placebo groups. The AEs most frequently associated with antroquinonol treatment by preferred terms (PTs) were diarrhoea (32.2%), nausea (6.7%), and vomiting (4.4%). There was an increasing trend in the incidence of diarrhoea as the dose of antroquinonol increased.

Two SAEs were reported in one subject receiving antroquinonol. The SAEs were not related to antroquinonol and did not cause study discontinuation.

There were no clinically meaningful findings in vital signs, physical examination, electrocardiogram (ECG), and laboratory assessments.

Overall, the results of this study showed a positive benefit-risk profile in favor of antroquinonol 100 mg in terms of lipid profile and arterial stiffness. The dosages of antroquinonol were generally well tolerated.

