difficulty in breathing), or chills/rigors, myalgia (muscle pain), headache, sore throat, and loss of taste or smell; other symptoms that could be related to COVID-19 will also be recorded.

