Any clinically significant abnormal laboratory findings or other abnormal safety assessments which are associated with the underlying disease under study, unless judged by the investigator to be more severe than expected for the participant's condition.

The disease being studied or expected progression, signs, or symptoms of the disease being studied, unless more severe than expected for the participant's condition.

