### 7.4 Baseline Disease Characteristics

Baseline disease characteristics will be listed and summarized by treatment group and overall for the ITT set. Standard descriptive statistics will be presented for the continuous variables of:

- oxygen saturation (SpO2) (%);
- WHO COVID clinical improvement ordinal scale.

The total counts and percentages of patients will be presented for the categorical variables of:

- patient setting;
- chest imaging result (normal, abnormal NCS, abnormal CS);
- SARS-CoV-2 test result (negative, positive);
- WHO COVID clinical improvement ordinal scale (at or below each score);
- COVID-19 symptoms;
- COVID-19 symptoms – maximum severity;
- patients with diarrhea.

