### **7.6.2.4 Vital Status, Patients Alive and Free of Respiratory Failure, and COVID-19 Symptoms**

Proportion of patients with vital status of death in both groups on Days 7, 14, and 28 will be summarized compared using the same logistic regression model as the primary model.

Proportion of patients alive and free of respiratory failure on Days 7 and 28 will be summarized and compared using the same analysis as the primary endpoint.

Proportion of patients with each COVID-19 symptoms at baseline and on Days 7, 14, and 28 will be summarized and compared using logistic regression following the same method as the primary endpoint. Shift from baseline in severity table for each COVID-19 symptoms will be provided by treatment group.

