### 7.7.2 Adverse Events

All adverse events (AEs) recorded on the eCRF will be coded using the MedDRA dictionary [Version 23.0 dated 19 Apr 2020 or a later version if updated during the study (exclusively meant for COVID-19)] and classified as either pre-treatment AEs or treatment – emergent AEs (TEAEs) as follows:

- Pre-treatment AEs are events that start after the signing the informed consent form and prior to the date of first dose of study treatment.
- TEAEs are events with start date on or after the date of first dose of study treatment and up to 2 weeks after date of last dose of study treatment or events with start date prior to the date of first dose of study treatment whose severity worsens on or after the date of first dose of study treatment.

If an AE can't be classified as pre-treatment AE or TEAE due to missing/partial dates, it will be classified as TEAE.

The number and percentage of patients reporting each pre-treatment AE will be summarized for each treatment group and overall, by System Organ Class (SOC) and Preferred Term (PT) for SS.

All AE data will be listed by treatment group and overall. Treatment-emergence status will be flagged in the listing. In addition, corresponding listings of serious AEs (SAEs), treatment-related AEs, AEs leading to discontinuation of study treatment, AEs leading to discontinuation of study and AEs resulting in death will be produced for the SS.

The severity of all AEs is recorded as mild, moderate, or severe. If severity is missing for a TEAE, it will be considered severe only in the overall category in the summary tables.

The relationship between an AE and treatment is assessed as related, possibly related, unlikely related, or not related. A treatment-related AE is an AE considered by the investigator as related or possibly related to treatment or with missing relationship to treatment.

An overview table will summarize the number and percentage of patients with at least one of the following TEAEs, along with the number of corresponding TEAEs, where

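### New diarrhoea, nausea or vomiting after first dose may be missed in the AE tables, because the protocol's two rules on disease symptoms disagree and nothing links the symptom form to the AE form

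*Protocol*

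**What the plan says.** - **Symptom form.** Protocol section 7.1.2.7 lists dry cough, dyspnea, chills or rigors, myalgia, headache, sore throat, and loss of taste or smell. It then adds that "other symptoms that could be related to COVID-19 will also be recorded".
- **AE rules.** Protocol Appendix 1, under *Definitions*, takes in any untoward occurrence, related to the drug or not, and leaves out disease symptoms only if they were ongoing before entry and do not worsen unexpectedly. Under *Events not to be reported as adverse events*, the same appendix exempts the disease itself and its expected progression, signs or "symptoms of the disease being studied, unless more severe than expected for the participant's condition". This second exemption is not limited to symptoms present at entry. It also lacks the exception for drug-related events that the same subsection attaches to its two respiratory items.
- **AE tables.** SAP section 7.7.2: "All adverse events (AEs) recorded on the eCRF will be coded using the MedDRA dictionary". Nothing there brings in entries from the symptom form.
- **Symptom analysis.** SAP section 7.6.2.4, a secondary efficacy section, compares each symptom on Days 7, 14 and 28 by logistic regression, and adds: "Shift from baseline in severity table for each COVID-19 symptoms will be provided by treatment group".
- **Diarrhoea at baseline.** Exclusion criterion 15 bars it whatever the cause, yet SAP section 7.4 lists "patients with diarrhea" among the baseline disease characteristics.
- **Known effect of the drug.** Protocol section 1.2.3 reports diarrhoea in 32.2%, nausea in 6.7% and vomiting in 4.4% on antroquinonol in the hyperlipidemia study. It adds: "There was an increasing trend in the incidence of diarrhoea as the dose of antroquinonol increased". Diarrhoea was also the most frequent AE on placebo; that rate is not given.

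**The concern.** Because diarrhoea at baseline is an exclusion, diarrhoea during treatment in an eligible patient should be new. A blinded investigator often cannot tell whether it comes from the drug or from COVID-19. Under the definitions in Appendix 1 it is an AE. Under the later exemption, if the site regards it as an expected symptom of the disease, it is not to be reported as one. The open field on the symptom form then gives it another place to be recorded, and no reconciliation or pooled table brings it back.

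At stake is the tolerability description for the effect most often seen with this drug. Safety is a stated secondary objective, and the AE tables are where a reader will look for gastrointestinal events. The primary endpoint is not affected.

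**Working it through.** **1. The earlier figures.** In the hyperlipidemia study "30 each were randomly assigned to the placebo, antroquinonol 50 mg, antroquinonol 100 mg, and antroquinonol 150 mg groups", so 3 × 30 = 90 patients had antroquinonol. The reported percentages fit whole counts: 29/90 = 32.2%, 6/90 = 6.7%, 4/90 = 4.4%. The counts are inferred; the protocol gives only percentages.

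**2. The route, rule by rule, for diarrhoea starting on Day 4.**
- Appendix 1, *Definitions*: not ongoing before entry, so it is an AE whatever its cause.
- Appendix 1, *Events not to be reported*: if judged an expected COVID-19 symptom and no more severe than expected, it is not reported as an AE.
- Protocol 7.1.2.7: it can be entered as another symptom possibly due to COVID-19.
- SAP 7.7.2: if no AE was entered, it is in no AE table.
- SAP 7.6.2.4: it may or may not be tabulated, because the SAP does not say whether free-text entries count among the symptoms compared.

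**3. Size, as an illustration.** Inputs: 174/2 = 87 per arm; p = 0.322 on antroquinonol, carried over from the earlier study; f = the share of patients with diarrhoea entered only on the symptom form, the same in both arms. The documents do not give f.

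Expected antroquinonol patients with diarrhoea in the AE tables = 87 × 0.322 × (1 − f):
- f = 0: 87 × 0.322 = 28.0
- f = 25%: 28.0 × 0.75 = 21.0
- f = 50%: 28.0 × 0.50 = 14.0

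Absolute difference shown = (32.2% − q) × (1 − f), where q is the placebo rate. It is not given, so a range is assumed:

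| q | f = 0 | f = 25% | f = 50% |
|---|---|---|---|
| 5% | 27.2 points | 20.4 | 13.6 |
| 10% | 22.2 | 16.65 | 11.1 |
| 20% | 12.2 | 9.15 | 6.1 |

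The risk ratio does not move, because (1 − f) cancels. At q = 10% it is 32.2/10 = 24.15/7.5 = 16.1/5 = 3.22 at each value of f.

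**4. Limits of the carried-over rate.** The earlier study gave 50, 100 or 150 mg once daily for 12 weeks; this trial gives 100 mg twice daily for 14 days. The 14-day rate could be lower or higher than 32.2%.

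**The case against.** The strongest reply is that the AE system, read as a whole, already catches these events. The AE definition is broad. AEs are elicited by separate nonleading questions (Protocol 7.2.1.1), and the causality scale has grades for events due to the patient's condition and for events that could be due to either. Entry on both forms is not barred. The exemption covers only expected symptoms, and no passage names diarrhoea, nausea or vomiting as expected in COVID-19. Protocol Table 1 has capsules taken after food to limit gastrointestinal effects, which points sites towards the drug. All of this stands, and it means that f may be zero. It does not remove the exemption, which a site can follow as written.

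Stronger readings are tempting but not supported:
- *The toxicity is under-counted.* The documents show that loss is possible, not that it happens.
- *Dose-related gastrointestinal harm.* The dose trend is stated for diarrhoea only. With the placebo rate missing, the excess over placebo is unknown.
- *Drug diarrhoea is analysed as efficacy.* Other symptoms are only said to be recorded. SAP 7.4 lists diarrhoea apart from COVID-19 symptoms, which may simply be a check on exclusion 15. If free-text entries are analysed, the severity shift table by arm would show an excess.
- *Loss of power to detect the difference.* SAP 7.7.2 rules out statistical comparison of AEs, so there is no test to lose power. Equal loss in both arms leaves the risk ratio intact.
- *The enrollment pause rule is disabled.* Protocol 4.5 counts treatment-related events. The only loss would be events that would have been rated at least possibly related had they been entered as AEs.

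**Conclusion.** The point holds as a possible omission. Two parts of Protocol Appendix 1 give different answers for a new symptom that resembles the disease, an open symptom field can receive it, and the AE tables do not look there. If a share f is entered only as symptoms, the expected 28 of 87 antroquinonol patients with diarrhoea becomes 21 at f = 25% and 14 at f = 50%, and the absolute difference between arms shrinks by the same fraction. These figures assume that the 12-week once-daily rate carries over and that f is equal in both arms, which blinding makes reasonable. Neither f nor the placebo rate can be derived from the documents. This is a cheap improvement to the tolerability description; it does not touch the primary analysis.

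**What to change.** 1. **Protocol Appendix 1.** Reconcile the definitions with the list of events not to be reported, so that sites have one rule for disease-like symptoms that begin after entry.
2. **SAP 7.7.2.** Add one descriptive Safety Set table by arm: patients with diarrhoea, nausea or vomiting recorded after first dose on either the AE form or the COVID-19 symptom form, including free text. Count an entry if the symptom was absent at baseline or is more severe than at baseline. Count each patient once, at maximum severity where severity was recorded. For symptom entries the comparison has to be by visit, because the documents describe no onset date. Use all post-dose symptom visits in the schedule, not only Days 7, 14 and 28.
3. **SAP 7.6.2.4.** State that free-text gastrointestinal symptoms are not interpreted as efficacy outcomes.

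Cost: a wording clarification, one table, and coding of the free-text symptoms if that is not already planned. The eCRF was not among the documents, so the fields need checking. No assessment or treatment changes. Downside: gastrointestinal symptoms caused by COVID-19 raise the count in both arms; randomization should balance these, and the AE tables remain alongside.

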7.1.3. Exploratory efficacy endpoints

The exploratory efficacy endpoints include:

- Covariates of age, sex, and remdesivir or other authorized treatments for COVID-19 use at baseline
- Use of any new authorized treatments recommended as SoC for COVID-19 during the course of the study

The final list of covariates for subgroup analyses are as detailed in the final statistical analysis plan.

New authorized treatments to be analyzed will be identified post hoc and will be collected from the concomitant medications eCRF page.

7.2. Safety Assessments

7.2.1. Adverse events

7.2.1.1. *Definitions*

Adverse event definitions and assignment of severity and causality are detailed in [Appendix 1](#).

Adverse events will be elicited from the patient (or, when appropriate, from a caregiver, surrogate, or the patient's legally authorized representative) by the study site staff using a nonleading question such as "How are you feeling today?" or "Have you had any health concerns since your last visit?"

The investigator and any designees are responsible for detecting, documenting, and reporting events that meet the definition of an AE or SAE and remain responsible for following up AEs that are serious, considered related to the study treatment or the study, or that caused the patient to discontinue the study treatment.

Adverse events will be assessed from signing the ICF until 2 weeks after the last dose of study treatment (Day 28 ± 2 days) as noted in the Schedule of Assessments table ([Appendix 5](#)).

Adverse events will be coded according to the Medical Dictionary for Regulatory Activities (MedDRA) version 23.0 dated 19 April 2020 (exclusively meant for COVID-19) or later.

7.2.1.2. *Reporting serious adverse events*

Serious AE reporting will be carried out as per local/country regulations, and will be described in the Safety Management Plan.

All SAEs occurring after the signing of the ICF until 30 days following last dose of the study treatment and regardless of study treatment relationship, must be reported to Covance within 24 hours of obtaining knowledge of the event. The report should include all available information requested on the SAE form.

Serious AEs - Covance PSS

E-mail: [contact] (standard)

The SAE form will collect data surrounding the event (eg, the nature of the symptom[s], time of onset in relation to initiation of therapy, duration, intensity, and whether or not therapy was discontinued). The investigator's assessment of the probable cause of the event will also be included. In addition, relevant medical history, concomitant medications, laboratory and diagnostic tests reports, and procedures as well as all pertinent medical information related to the event will also be collected.

Covance PSS will forward SAE queries requesting incomplete or missing information directly to the investigator. It is the investigator's responsibility to be diligent in providing this information back to Covance PSS as soon as it is available.

7.2.2. Pregnancy

Female patients of childbearing potential will take a pregnancy test during screening (or pretreatment on Day 1), discharge, ET/EOT, and at the Day 28 Follow-up/EOS visit. Additionally, local/country regulations will be followed as applicable (eg., a pregnancy test one month following the last dose of study treatment in female patients of childbearing potential).

A urine pregnancy test may be performed but must be confirmed with a serum pregnancy test (screening only). The Follow-up/EOS visit test will be a urine pregnancy test only (pregnancy test kit will be provided to the patient when discharged).

Following administration of study treatment, pregnancy cases in any patient who is a female of childbearing potential or female partner of a male patient will be reported if known until the patient completes or withdraws from the study. The pregnancy will be reported immediately by telephone and by faxing a completed pregnancy report to the sponsor (or designee) within 24 hours of knowledge of the event. The pregnancy will not be processed as an SAE; however, the investigator will follow the patient until completion of the pregnancy and must assess the outcome in the shortest possible time. Generally, the follow-up will be no longer than 6 to 8 weeks following the estimated delivery date.

The investigator should notify the sponsor (or designee) of the pregnancy outcome by submitting a follow-up pregnancy report. If the outcome of the pregnancy meets the criteria for immediate classification of an SAE (eg, spontaneous or therapeutic abortion [any congenital anomaly detected in an aborted fetus is to be documented], stillbirth, neonatal death, or congenital anomaly), the investigator will report the event by telephone and by faxing a completed SAE form to the sponsor (or designee) within 24 hours of knowledge of the event.

